Inclusion of Incarcerated Individuals: Incarcerated individuals will not be included in this study.

Inclusion of Minorities: We anticipate the racial-ethnic composition of the study sample to reflect that of the clinical population. If the proportion of minority women falls significantly below this anticipated number, we will consider targeted recruitment procedures to achieve the projected representation.

5. Number of Subjects

Up to 75 subjects seeking prenatal care at the University of New Mexico will be enrolled. Subjects will be pregnant, age 18 years or older, and registered as outpatients. Pregnant women are included because the purpose of this study is to determine the feasibility of studying the use of an oral probiotic agent in healthy, low risk, GBS positive pregnant women at term. We also propose to explore the effect of the probiotic on maternal GI symptoms and identify significant barriers to probiotic use in our population. Other special classes of subjects such as children, prisoners, and institutionalized individuals will not be enrolled.

This includes low risk patients seeking prenatal care at the University of New Mexico. Approximately 1500 women received prenatal care in the UNM Midwifery and OBGYN clinics in 2019 and approximately 20% were colonized with GBS. This gives us an adequate population from which to draw our study sample. We anticipate screening approximately 150 subjects over 8 months to allow us to enroll up to 75 subjects for our study after screening failures. A 30% dropout rate has been incorporated into sample size estimation to account for development of risk factors or failure to follow study procedures. These estimates are derived from Marquette University's randomized control trial pilot study of probiotics in pregnancy conducted at Marquette University and their current NIH funded double-blind randomized-controlled trial of Florajen3 to reduce GBS antenatal colonization. Tricore Lab has verified a 20% positive rate of GBS in our prenatal study population. For this open-label randomized control trial and feasibility study, a total sample of up to 75 participants will be targeted for enrollment and will be randomized to either the intervention group (receiving probiotics) or routine care (no intervention). A 30% dropout rate is assumed based on a preliminary study conducted at Marquette University; therefore, we anticipate that approximately 50 participants will

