Outcome Variables	Study Data Collection Research staff will document data from all measures on the Summary Data Collection Form.	T1 Baseline 36-37 ^{6/7}	T2 Admission to L&D	T3 Postpartum Day 0-14	T4 2 weeks postpartum	T5 6 weeks postpartum
	Procedures					
Qualitative GBS Colonization (+ or -)	Vaginal-rectal GBS swab.		X			
Intervention Adherence [Probiotic group only]	Final Capsule Count			X		
Maternal GI Symptoms	Antepartum Gastrointestinal Symptom Assessment (AP-GI-SA-10)	Х		Х		

Version Date: 12/2/2021

Adverse Events	Adverse Event Solicitation and Documentation Form [Prenatal providers will also solicit for adverse events at all prenatal visits between study visits]		X	X	X
Demo- graphics	Demographic Questionnaire	X			
Lifestyle practices: sexual, hygiene, diet	Questionnaire for Participants	X	X		
Future Feasibility Form					X

Version Date: 12/2/2021

Timeline for Completion of the Project

Timeline for Completion	on of the froject
June 2020	-IRB submission -Planning for meetings with division partners (nursing, medical assistants, midwives, OBs, lab) -Create recruitment tools, handouts, posters -Complete translation of all study materials into Spanish -Upload all final questionnaires into the UNM REDCap system, study projectEstablish safe storage procedures for probiotics prior to distribution to participants -Request probiotic shipment from Florajen
July/August 2020	-Work with research staff and clinical partners on protocols for the 2nd GBS swab collection at T2 -Establish protocols for testing and billing of T2 study swabs with UNM Tricore lab -Receive probiotics from Florajen -Orient research staff to project & create parameters for EHR use for tracking patients -Present study at division meetings of partners (residents, clinic staff, faculty, L&D staff, lab) -Receive iPads from Marquette and add data collection forms to the UNM REDCap system.
September 2020	Start recruitment and data collection
April 2021	End recruitment
May 2021	-Final data collection -Begin data analysis in collaboration with Marquette University
May-September 2021	-Data Analysis -Submit for poster presentation at professional conference(s)
Fall 2021	-Grand Rounds Presentation -Development of poster presentation -Write a paper and submit for publication in peer reviewed journal

7. Study Endpoints

Our primary outcome variable is qualitative GBS colonization (positive versus negative), at the time of labor admission.

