For the continuous variables measured more than a single time (i.e. GI symptoms) the data analysis method will be latent change score model (LCM). This allows us to estimate the mean and standard deviation of the change between time points. By adding the group into the LCM, we will test the group mean difference in the change over time between the treatment and placebo groups. This will test the significance and clinical relevance (effect size) of the treatment over time. For the binary variable (qualitative GBS colonization), we will use logistic regression, with the baseline GBS colonization and treatment group as predictors. This would allow to test differences in the likelihood of being GBS positive, controlling for their initial status. The clinical relevance can be evaluated with the effect size Odds Ratio. For all the analyses, relevant demographic characteristics, hygiene practices, adherence, and birth characteristics identified in the first step will be added as covariates, to account for their possible influence in outcomes of interest.

14. Provisions to Monitor the Data to Ensure the Safety of Subjects

Risk Management and Emergency Response. If any study participant has a fever or other signs of infection, they will be instructed to contact the clinic or OB Triage, as is the usual process for pregnant women. Subjects will be provided with the PI contact information in the event that they need to call after hours. In the case of emergency, such as severe illness, the subjects will be instructed to call OB Triage and seek care in the University of New Mexico system whenever possible. Patient participation in the research study will be noted in the antenatal problem list; any healthcare provider who cares for the patient will have knowledge of study participation. Although highly unlikely, if it is determined that a subject has a clinical infection due to any component of Florajen Digestion Howaru® Dophilus-Lactobacillus acidophilus NCFMTM; Lactobacillus acidophilus La-14; floraFIT Bifidobacterium lactis Bi-07TM; Bifidobacterium animalis ssp. Lactis HN019, floraFIT Bifidobacterium longum Bl-05TM, as determined by culture and strain-typing, standard medical care will be provided to

Page 18 of 31 Version Date: 12/2/2021

the subject. No such emergencies occurred during the pilot testing or during NIH/NICHD funding R21HD095320 that is in progress under IND#16549 at the time of this application.

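### The two-visit GI symptom score is to be analysed with a latent change score model in about 50 women; fitted in the usual way, its nominal 5% test would run at about 6% to 7%, and a t-based linear regression does the same job correctly

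*Combined protocol and SAP*

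**What the plan says.** Section 13 (Data Analysis) covers continuous variables measured more than once and gives GI symptoms as the example. For these, "the data analysis method will be latent change score model (LCM"). The test is described as follows: "By adding the group into the LCM, we will test the group mean difference in the change over time". The result is meant to show both significance and effect size.

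The instrument is the "Antepartum Gastrointestinal Symptom Assessment (AP-GI-SA-10"). The data collection table in Section 6 schedules it twice: at T1 (baseline) and T3 (postpartum day 0-14).

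Section 13 also says, for all analyses, that relevant variables "identified in the first step will be added as covariates". They come from four families: demographics, hygiene practices, adherence and birth characteristics. The first step is a logistic regression of group assignment on these variables. No retention threshold or maximum number is given.

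On sample size, Section 5 says "a total sample of up to 75 participants will be targeted for enrollment" and "A 30% dropout rate is assumed based on a preliminary study conducted at Marquette University", from which "we anticipate that approximately 50 participants will" complete the study.

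For the GI test, the documents state no estimator, software, reference distribution (z or t), small-sample correction or alpha.

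**The concern.** A latent change score model is useful when several indicators per visit allow measurement error to be separated from true change. With one total score at each of two visits there is no measurement model to fit. The model is just-identified, its change variable is the observed difference, and its group effect is the coefficient on arm in a regression of that difference on arm and covariates.

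What remains is the way such models are usually fitted. Maximum likelihood divides the residual sum of squares by N rather than by the residual degrees of freedom, and the z-test uses normal rather than t quantiles. In a large trial neither matters. With about 50 women both make the interval too narrow, and the first grows worse with each covariate.

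At stake is the p-value and interval for a named secondary outcome and stated aim (Sections 1, 3 and 7). Because the trial is meant to inform a larger one, an interval that is too narrow would overstate how precisely the GI effect is known.

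**Working it through.** **The plan's own figure.** 75 × (1 − 0.30) = 52.5, or 52 whole completers, which agrees with the stated figure of approximately 50. The documents give no error rate or power for the GI analysis.

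**Inputs.**
- From the documents: n = 50 completers (Section 5), with 52 and 75 as alternatives; two measurements per woman (Section 6 table); covariates as flagged in the first step (Section 13).
- Assumed, because not stated: one total score per visit, maximum likelihood with z-tests, a two-sided 5% level, normal errors, and k covariates with k from 0 to 10 or 11. The allocation ratio does not affect the result.

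**Formula for the false-positive rate.** With residual degrees of freedom df = n − 2 − k, the maximum-likelihood z statistic equals the ordinary t statistic multiplied by √(n/df). Hence

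true size = 2 × P(t_df > 1.96 × √(df/n)).

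For k = 0: df = 48 and the effective cut-off is 1.96 × √(48/50) = 1.92, giving 6.1%. For k = 3: df = 45 and 1.96 × √(45/50) = 1.86, giving 7.0%. For k = 10: df = 38 and 1.96 × √(38/50) = 1.71, giving 9.6%.

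**Formula for the interval.** Width relative to the correct t interval = 1.96 × √(df/n) / t_df,0.975. For k = 0 this is 1.920/2.011 = 0.955 (4.5% too narrow). For k = 3 it is 1.859/2.014 = 0.923 (7.7% too narrow).

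| Covariates k (n = 50) | True size, formula | True size, simulation (40,000 trials) | Interval too narrow by | Size with t and residual df, simulation |
|---|---|---|---|---|
| 0 | 6.1% | 6.0% | 4.5% | 4.9% |
| 3 | 7.0% | 6.6% | 7.7% | 4.7% |
| 5 | 7.6% | 7.8% | 9.9% | 5.1% |
| 10 | 9.6% | 9.5% | 15.6% | 5.0% |

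At k = 11 the formula gives 10.0%.

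**How many covariates?** Only variables flagged as related to group assignment are to be added, and under randomisation few should be. In a simulation with 10 independent candidates in a joint logistic model at n = 50, the average number kept was 0.6 at p < 0.05, 1.3 at p < 0.10 and 2.4 at p < 0.20. That corresponds to a true size of about 6.2% to 6.8%.

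**Sensitivity.** For k = 0 to 10, the size is 6.0% to 9.3% at n = 52, and 5.7% to 7.7% if all 75 women contribute. A likelihood-ratio test in place of the z-test at n = 50 gives 5.6% (k = 0) to 9.0% (k = 10).

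**The case against.** **The plan names a model, not an estimator.** A t reference or a small-sample correction is neither planned nor excluded, and the 5% level is not written down. This stands: every error rate here is conditional on the usual fit, and the documents do not show that the test will be wrong.

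**The upper end needs many covariates.** A reader might infer a rate of about 10% from the four families of candidate variables. The documents do not support that as the expected figure, because only variables flagged in the first step enter, and 10% needs about 11 of them. It is not ruled out, since the plan sets no threshold or cap, but 6% to 7% is the better-supported figure.

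**Fifty may be pessimistic.** The assumed dropout includes women who develop risk factors or do not follow procedures (Section 5). Some could still answer the T3 questionnaire, which Section 6 plans for every participant. This stands, and it lowers the range to 5.7% to 7.7% if all 75 contribute.

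**The covariates do most of the damage.** With arm alone the excess is about one percentage point. This is correct, and the fix must therefore limit the covariates as well as change the reference distribution. A t-based or small-sample-corrected test within the change model would also cure the error rate. Replacing the model is preferred because the latent structure brings nothing in return.

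**Item-level modelling.** A reader might also infer that the ten items would be indicators at each visit, with about 55 parameters for about 50 women. Section 13 specifies no such model, so this is hypothetical and no figure above relies on it.

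**Conclusion.** The concern holds in a limited form. For a single score measured twice, the planned model is equivalent to a regression of change on arm and covariates. Under the usual maximum-likelihood fit with z-tests at a two-sided 5% level, the true false-positive rate in about 50 women is roughly 6% to 7% with zero to three covariates. The excess is always in the anti-conservative direction and grows with each covariate.

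The importance is low. GI symptoms are a secondary outcome of a feasibility pilot, Section 5 describes this aim as exploratory, and no decision rule depends on the p-value. It should not be read as a threat to the primary GBS comparison, which Section 13 analyses by a separate logistic regression.

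**What to change.** In Section 13, replace the latent change score model for GI symptoms with a linear regression of the T3 AP-GI-SA-10 score on randomised arm, with the T1 score as covariate. Naming the T3 visit and keeping the T1 score matter: a bare regression of the GI score on arm could be read as discarding the baseline.

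Allow only a small set of further covariates, all measured at baseline and listed in advance, in place of those chosen by the first-step screen. State the alpha level, and take the p-value and 95% interval from the t distribution with the residual degrees of freedom. If the latent change model is kept, report it only as a secondary check and do not base the claim on its z-test.

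The cost is a sentence or two in Section 13 and no new data. The stated interval becomes slightly wider, which is the correction intended. Women without a T3 score do not enter the model, but in a two-visit model a T1 score alone adds almost nothing to the estimated arm effect.

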Participant flow through the study: Healthy adult pregnant women, who are GBS positive, at \geq 36 weeks gestation, will be introduced to the study. If they express an interest in the study, the research coordinator will conduct a prenatal chart review after their GBS swab result has returned and review study inclusion and exclusion criteria for each interested woman by completing the Prenatal Eligibility Screening Form (PESF). For a woman who is eligible and willing, the research coordinator will complete the informed consent. Participants will provide written or e-signed consent at 36.0 to 37.6 weeks gestation. Consented participants will be randomized to one of two groups, standard of care/control group or the intervention group. Participants in the intervention group will begin taking oral study capsules once daily from time of enrollment/randomization at \geq 36 weeks gestation until the time of birth. The research staff member will sequentially distribute the pre-labeled bottles of study capsules to the intervention group, one bottle of 30 Florajen Digestion probiotic capsules to women in the intervention group at the time of randomization. Because women are seen on a

Page 16 of 31 Version Date: 12/2/2021

weekly basis in late pregnancy, generally we anticipate that participants will receive the probiotic at enrollment; their next regularly scheduled prenatal appointment at approximately 37 weeks gestation. For women who do not attend this appointment in person, research staff can also arrange to meet participants at the prenatal clinic site to initiate the intervention between prenatal appointments. This will be arranged at the woman's convenience. Subjects in the control group will not receive any capsules and will be advised to continue their routine prenatal self-care. All subjects in the intervention group will be instructed to keep the study bottle in the refrigerator and to take one capsule per day until they give birth and to bring the bottle with them to the hospital at the time of labor.

All participants will complete baseline forms: Antepartum Gastrointestinal Symptom Assessment (AP-GI-SA-10), Demographic Questionnaire and the Questionnaire for Participants.

Research coordinators will be filling out a Summary Data Collection Form (SDCF) on all study participants.

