At the time of labor admission to Labor and Delivery, participants will receive a vaginal-rectal GBS swab as a part of the research study. This is not standard of care and thus participants will receive this in addition to the standard of care. The results of the GBS swab will be collected for study purposes only.

All participants regardless of group assignment will receive the usual standard of care for GBS positive status and will be given intrapartum antibiotic prophylaxis (IAP) per protocol during labor.

All participants on postpartum day 0-14, in the hospital will answer these questionnaires: Antepartum Gastrointestinal Symptom Assessment (AP-GI-SA-10), Adverse Event Solicitation and Documentation Form (only for themselves, not their newborn(s)) and Questionnaire for Participants.

*we will not collect Adverse Event Solicitation and Documentation during this study time point because if the information is collected on postpartum day 0, there would be no way of reporting an adverse event for the newborn(s) at this time.

For the intervention group on postpartum day 0-14, study staff will conduct a final capsule count.

All participants at their 2 weeks postpartum visit will have an Adverse Event Solicitation and Documentation Form completed which will also include Adverse Event Solicitation and Documentation for their newborn(s).

Page 17 of 31 Version Date: 12/2/2021

All participants at their 6 weeks postpartum visit will have an Adverse Event Solicitation and Documentation Form & Future Feasibility Form completed which will also include Adverse Event Solicitation and Documentation for their newborn(s).

13. Data Analysis

Demographic characteristics for the full sample and each group will be presented. Logistic regression will be used to identify if the group assignments have relationships to variables such as demographic characteristics, hygiene practices, adherence, and birth characteristics. Logistic regressions test if any of these variables can predict the group that the participants were in. Another advantage of logistic regression is that by adding all the predictors at the same time, we can state the effect of each one controlling for the other predictors, presenting a stronger test of group independence.

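### Section 13 selects covariates by whether they predict randomised group and names adherence, which exists only in the probiotic arm, so the primary model is undetermined and can answer the wrong question

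*Combined protocol and SAP*

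**What the plan says.** Section 13 (Data Analysis) works in two steps.

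- **Step 1** regresses randomised group on demographics, hygiene practices, adherence and birth characteristics. Its purpose is explicit: "Logistic regressions test if any of these variables can predict the group that the participants were in". The predictors enter jointly: "by adding all the predictors at the same time, we can state the effect of each one controlling for the other predictors".
- **Step 2** carries the result forward: "For all the analyses, relevant demographic characteristics, hygiene practices, adherence, and birth characteristics identified in the first step will be added as covariates". This covers the GI-symptom change model and the primary outcome, which Section 7 defines: "Our primary outcome variable is qualitative GBS colonization (positive versus negative), at the time of labor admission".

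Before covariates, the model for the binary outcome is a logistic regression on baseline GBS colonization and treatment group.

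The data collection table in Section 6 labels the adherence row "Intervention Adherence [Probiotic group only". Section 12 (Study Procedures) agrees: "For the intervention group on postpartum day 0-14, study staff will conduct a final capsule count", and "Subjects in the control group will not receive any capsules". Section 13 gives no adherence value for controls, no test and no threshold for being identified.

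Section 25 (Consent Process) lists the birth characteristics: mode of birth, membrane status before the swab, birth weight, length, head circumference, and Apgar scores at three times. The lifestyle questionnaire is given at baseline and again after birth ("All participants on postpartum day 0-14, in the hospital will answer these questionnaires"). Section 13 does not say which answers supply the hygiene covariates.

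**The concern.** Group is assigned by a computer-generated table. Testing a true baseline variable against group can therefore detect only chance imbalance, and it does not show whether the variable predicts GBS status.

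For variables that arise after assignment the rule is worse, because it favours whatever the assignment itself produced. Adherence is the clearest case: it exists only because a woman was given capsules.

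At stake is the primary estimate. Depending on how controls are coded and which test is used, the same text leads to no estimable model, a treatment-only model, treatment plus adherence, or treatment plus birth characteristics. Section 6 says that investigators and research staff are not blinded, so the choice could be made with group known. Section 14 also plans a formal interim efficacy analysis, and no other efficacy model is given for it.

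**Working it through.** **Inputs from the protocol.** Up to 75 enrolled, 30% dropout, approximately 50 completers (Section 5). All participants GBS positive at entry (Section 4). From Section 2: mean compliance of 87% in one cited RCT; pilot adherence of 68% in two GBS-positive women and 90% in eight GBS-negative women; 21/49 versus 9/50 in another cited RCT, read here as conversion to GBS negative.

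**Assumptions not in the protocol.** 1:1 allocation, 25 completers per arm, adherence SD of 10-20 points, two-sided 0.05.

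**1. The plan's own figure.** 75 × 0.70 = 52.5, consistent with approximately 50 completers. No power calculation is stated, so there is none to reproduce.

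**2. Controls missing on adherence.** Complete cases are the probiotic arm only. Step 1 then has a constant outcome. In an outcome model with intercept, group and adherence, the first two columns are identical, so the rank is 2 of 3 and the treatment effect cannot be estimated.

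**3. Controls coded 0, every probiotic participant taking some capsules.** Adherence separates the arms.
- Adherence alone: the null log-likelihood is 50 × ln(0.5) = −34.66 and the fitted one tends to 0. The likelihood-ratio chi-square is 2 × 50 × ln 2 = 69.3. The Wald p-value is about 1, because the standard error diverges.
- Joint step 1, simulated with three other predictors, one imbalanced by 1 SD: without adherence, the imbalanced predictor has a median z of about 2.9. With adherence, no predictor's |z| exceeds 0.0205. The likelihood-ratio chi-square is about 55 for adherence and below 0.00001 for the imbalanced predictor.

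The likelihood-ratio test thus selects adherence and nothing else. The Wald test selects nothing, and the real imbalance is hidden.

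**4. If zero-coded adherence enters the outcome model.** In logit P(GBS positive) = a + b × group + c × adherence, b compares assignment to probiotic at zero capsules with control. With mean m and SD s in the probiotic arm, 1:1 allocation and zeros in controls, the variance inflation for group is 1 + m²/(2s²), and the standard error grows by its square root.

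| m | s | Inflation | SE factor |
|---|---|---|---|
| 0.68 | 0.20 | 1 + 0.4624/0.08 = 6.8 | 2.6 |
| 0.856 | 0.20 | 1 + 0.7327/0.08 = 10.2 | 3.2 |
| 0.87 | 0.20 | 1 + 0.7569/0.08 = 10.5 | 3.2 |
| 0.87 | 0.10 | 1 + 0.7569/0.02 = 38.8 | 6.2 |

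The 0.856 is the pilot arm mean: (2 × 68 + 8 × 90)/10 = 85.6%.

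**5. Illustration with one cited RCT's rates.** GBS positive: 41/50 = 82% versus 28/49 = 57.1%. OR = (28/21)/(41/9) = 0.29. At 25 per arm the normal approximation gives an unadjusted power of 47.9%, and simulation about 45-48%. With zero-coded adherence in the model, simulated power is 4-12% if the effect does not depend on capsules taken, and 2-3% if it is proportional to them.

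**6. Birth characteristics.** Eight are listed. With no true difference and independent tests at 0.05, the chance that at least one is selected is 1 − 0.95⁸ = 33.7%. Size measures and Apgar scores are correlated, so this is approximate.

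**7. The base model.** Baseline GBS is positive in everyone, so the term duplicates the intercept and the model is treatment only.

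**The case against.** The strongest reply is that the rule does not force adherence in. Section 13 offers the list as examples and restricts it to relevant variables. A sensible analyst would omit a variable that has no values in one arm, and the stated base model would remain. That stands in part. A reader might infer that the primary model cannot be fitted at all, and the protocol does not support this: only models containing adherence fail. But adherence is named in both steps, the base model is not designated as primary, and omitting adherence is a decision that the plan leaves open.

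Second, separation requires every probiotic participant to take at least one capsule. With one, two or three who take none, the likelihood-ratio chi-square for adherence alone is 60.8, 55.1 or 50.2. Adherence is still selected, but separation is no longer complete.

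Third, nothing says that controls would be coded 0, and all standard-error and power figures lie on that branch. The pilot adherence values also come from ten women taking Florajen3 from 28 to 36 weeks, not this product near term. Both points are right, and the figures are illustrations. The one-arm result in step 2 needs none of these inputs.

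Fourth, this is a feasibility pilot. However, GBS status at labor admission is its declared primary outcome, and an efficacy interim is planned.

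Finally, Section 13 mentions a placebo group, which this trial lacks. The text may have been carried over from elsewhere; that is a guess and would not cure the rule.

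**Conclusion.** The concern holds. Section 13 does not determine one primary model, and one route it permits estimates something other than the effect of assignment to probiotic. The one-arm failure follows from the design alone. The split between likelihood-ratio and Wald selection follows once controls are coded 0 and all probiotic participants take some capsules. On that branch the standard error rises about 2.6 to 6.2 times under the assumed means and SDs, and illustrative power falls from about 45-48% to about 2-12%.

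Three stronger readings are not supported:

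- **A missed power target.** The protocol states none, so the power figures show lost precision only.
- **A known direction of bias from adjusting for adherence.** The pilot contrast of 68% and 90% fits both an effect through capsules and better prognosis in adherent women. Odds ratios simulated under an assumed prognosis link are too unstable to report.
- **A measurable distortion from birth characteristics.** They are recorded after randomisation and can enter, but the size of the resulting distortion cannot be computed from the protocol.

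**What to change.** Reword Section 13 as follows.

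1. Delete prediction of group as the rule for selecting covariates.
2. Designate the comparison by assigned group as the primary analysis, and remove the constant baseline GBS term.
3. State that adherence enters no between-group model. Report it descriptively, or in an exploratory analysis within the probiotic arm.
4. Limit any adjustment in the primary and GI-symptom models to T1 variables listed in advance. The factors that Section 2 undertakes to address (sexual activity, vaginal cleansing, yogurt intake) are natural candidates, using T1 answers. Allow birth characteristics, such as membrane status before the swab, only in a labelled sensitivity analysis.

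The cost is a change of text, with no new data or visits. The downside is that chance imbalances found after the fact are handled only in sensitivity analysis.
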